## 11.4. Notification of Adverse Events

### Sponsor Notification:

The investigational center staff must report all AEs to Medtronic in a timely manner. All Severe Hypoglycemia, Severe Hyperglycemia, DKA, SAE, and SADE should be reported as soon as possible (desired within 24 hours of investigator or study coordinator awareness) to Medtronic. Refer to Table

4 below for Investigator Reporting Requirements. For the previously mentioned events, the AE eCRF will be completed with all known details as soon as possible, this will serve as notification to Medtronic. If the study database cannot be accessed due to technical problems, contact the sponsor via email at [[contact]](mailto:[contact]) and provide the known details of the event. Once the access issue has been corrected, the event should be entered onto an AE eCRF.

Source documents that support the event (e.g. clinic notes, hospital admission and discharge records, lab reports, EMT reports, ER/Urgent Care) should be provided to the sponsor via the Medtronic BOX safety folder. All source documents/medical records should be redacted. Each source page should be identified with the subject ID.

## **11.5. Expedited Safety Reporting Requirements**

Documentation of GCP office and EC notification of any safety event must be kept at the investigational center and a copy sent to the sponsor.

*It is the responsibility of the investigator to follow their EC reporting requirements.*

**Table 4. Investigator Reporting Requirements for AE and Device Deficiencies**

For the following events, reporting requirements are:	

Serious Adverse Events (SAE)

	
Investigators shall immediately adopt appropriate therapeutic measures for subjects, and simultaneously report to the management department of medical device clinical study in investigational center in written form. Management department of medical device clinical study shall report to:	
Medtronic	Immediately
Local food and drug regulatory authority and health and family planning competent authority of the province, autonomous region and municipality directly under the central government where the investigational center locates	Within 24 hours
EC	Within 24 hours/ per EC's requirements
For the following events, reporting requirements are:	

All other AEs

All Device Deficiencies

	
Investigators shall record all the AEs and device deficiencies occurred during the clinical study. Investigators shall analyze the reasons for the events with Medtronic and document the analysis result in written report, including the comments of continuing, suspending or terminating study, which shall be reported to the EC through management department of medical device clinical study in investigational center for review.	
To Medtronic	Submit in a timely manner

*Medtronic Confidential*

	after the investigator first learns of the event.
To EC	Per EC's requirements

NOTE: In case there is/are additional AE reporting requirement(s) and/or process(es) (e.g. internal hospital policy or province regulatory authority instruction, etc.), these specific AE reporting requirement and process must be documented in a separate cover.

**Table 5. Sponsor Reporting Requirements for AE and Device Deficiencies**

For the following events, reporting requirements are: 

• Serious Adverse Events (SAE)

• Device Deficiencies with SADE potential

	
Medtronic submits to:	
The food and drug regulatory authorities and health and family planning competent authorities at the same level	Within 5 working days upon being informed
Other investigational center and investigators participating in the study	As per local reporting requirement
EC	Timely report to EC of the clinical Research institution through management department of medical device clinical study

NOTE: In case there is/are additional AE reporting requirement(s) and/or process(es) (e.g. internal hospital policy or province regulatory authority instruction, etc.), these specific AE reporting requirement and process must be documented in a separate cover.

## 11.6. Causality Assessment

An AE is not automatically related to the study device or procedure simply because the subject is wearing the device and participating in the study. The event should be reviewed to determine if the device or study procedure could have possibly caused the event and therefore is related to the study device or procedure.

Causality assessment is the determination of the relationship between an AE and the device being studied. It is expected that the investigational center will review all elements surrounding the AE to properly assess the causality of the event to the study device or to a study procedure.

This review would include the subjects' description of the event, study device uploads and medical records (if applicable) from the treating facility. These records will be made available to sponsor.

Investigators should classify the relationship between the AE and the study device or study procedures using one of the five possible causality categories listed below:

- **Not related:** relationship to the device or procedures can be excluded when:
  - the event is not a known side effect of the product category the device belongs to or of similar devices and procedures
  - the event has no temporal relationship with the use of the investigational device or the procedures;
  - the event does not follow a known response pattern to the medical device (if the response pattern is previously known) and is biologically implausible;
  - the discontinuation of medical device application or the reduction of the level of activation/exposure - when clinically feasible – and reintroduction of its use (or increase of the level of activation/exposure), do not impact on the serious event;
  - the event involves a body-site or an organ not expected to be affected by the device or procedure;
  - the event can be attributed to another cause (e.g. an underlying or concurrent illness/ clinical condition, an effect of another device, drug, treatment or other risk factors);
  - the event does not depend on a false result given by the investigational device used for diagnosis, when applicable;
  - harms to the subject are not clearly due to use error;
  - In order to establish the non-relatedness, not all the criteria listed above might be met at the same time, depending on the type of device/procedures and the serious event.
- **Unlikely:** the relationship with the use of the device seems not relevant and/or the event can be reasonably explained by another cause, but a relationship to the device cannot be completely ruled out.
- **Possible:** the relationship with the use of the investigational device is weak. Alternative causes are also possible (e.g. an underlying or concurrent illness/ clinical condition or/and an effect of another device, drug or treatment). Cases where relatedness cannot be assessed should also be classified as possible.
- **Probable:** the relationship with the use of the investigational device seems relevant and/or the event cannot reasonably be explained by another cause.
- **Causal relationship:** the event is associated with the investigational device or with procedures beyond reasonable doubt when:
  - the event is a known side effect of the product category the device belongs to or of similar devices and procedures;
  - the event has a temporal relationship with investigational device use/application or procedures;
  - the event involves a body-site or organ that
    - the investigational device or procedures are applied to;
    - the investigational device or procedures have an effect on;
  - the event follows a known response pattern to the medical device (if the response pattern is previously known);
  - the discontinuation of medical device application (or reduction of the level of activation/exposure) and reintroduction of its use (or increase of the level of activation/exposure), impact on the event (when clinically feasible);
  - other possible causes (e.g. an underlying or concurrent illness/ clinical condition or/and an effect of another device, drug or treatment) have been adequately ruled out;
  - harm to the subject is due to error in use;

- the event depends on a false result given by the investigational device used for diagnosis, when applicable;
- In order to establish the relatedness, not all the criteria listed above might be met at the same time, depending on the type of device/procedures and the serious event.

**Example: A severe hyperglycemia AE with the following event description would have the following causality assessment for device relatedness:**

Improved glucose without an infusion set/site change	Not related
Changed infusion set with glucose improvement	Possible
Infusion set fell out, bent cannula, occlusion alarm	Causal relationship

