
Risks with the use of an insulin infusion pump may include the risk of malfunction of the components of the system (pump, software, infusion set and reservoir) as well as the risk of use error during use of the system. Device deficiencies or use errors can result in administration of too much or too little insulin which can lead to the following clinical consequences:
 

• Hypoglycemia

• Hyperglycemia

• Diabetic ketoacidosis

• Severe hypoglycemia with or without associated seizure, coma or death

• Kinked cannula leading to hyperglycemia

• Infusion set disconnection from pump leading to hyperglycemia

• Subject removes the reservoir from the pump but forgets to disconnect the infusion set from the body which results in hypoglycemia or severe hypoglycemia

• Dislodged cannula leading to hyperglycemia

	
Prevention and mitigation include:
 

• Follow the provided user guides & instructions for insulin pump management which includes information on infusion set change.

• Training prior to study on device use and diabetes management principles and told to call with problems.

• Check SMBG 4-6 times a day and also before driving (as applicable). Instructed to have glucose on hand for hypoglycemia

• Change infusion set if suspected catheter occlusion or administer insulin with syringe for persistent hyperglycemia especially if ketones develop.

• A pump error may lead to under delivery or over-delivery of insulin

• Battery failure – no insulin delivered

• Insulin deterioration leading to hyperglycemia

• Incomplete priming; fails to prime tubing and/or cannula, leading to hyperglycemia

• Remove a reservoir, without suspending and reconnecting after a while resulting in a Hypoglycemia

• Patient not filling pump reservoir when needed leading to hyperglycemia

• Magnetic Resonance Imaging resulting in pump transmitter malfunction

• Inaccurate insulin delivery due to sudden altitude changes.

• Hypoglycemia or hyperglycemia from manual bolus

• Hypoglycemia or Hyperglycemia from the use of the Auto Mode feature where sensor glucose values may be used to calculate insulin bolus amounts

• Hypoglycemia or hyperglycemia from computer hacking

	

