
 
• Hypoglycemia
 
• Severe hypoglycemia
 
• Hyperglycemia
 
• Diabetic ketoacidosis User Entry Error             
 
◦ Patient administering boluses by entering false carb doses leading to hypoglycemia or hyperglycemia
 
◦ Patient entering false glucose values for any reason leading to hypoglycemia and hyperglycemia
 
◦ Patient entering false BG values for calibration leading to hypoglycemia or hyperglycemia
 
 
 
• Sensor failure resulting from patient failure to calibrate leading to hypoglycemia or hyperglycemia
 
• Sensor over-reading resulting in hypoglycemia
 
• Sensor under-reading resulting in hyperglycemia
 
• Sensor missed transmission, or any other fault resulting in no SG value, leading to hyperglycemia or hypoglycemia
 
• Voluntary insulin delivery (with the pump or with a syringe) immediately prior to entering Auto Mode may result in severe hypoglycemia despite shutting down insulin delivery by the algorithm
 
• Hypoglycemia related to patient taking insulin via injection while in Closed Loop (Auto Mode)
 
• Hypoglycemia or hyperglycemia related to entering or exiting Closed Loop (Auto Mode)
 
• Insulin over-delivery due to potential interference from acetaminophen
 
• Cyber security hacking into pump
 
	
 
• Follow the provided user guides for insulin pump management.
 
• Training prior to study on device use and diabetes management principles and told to call with problems.
 
• Check SMBG 4-6 times a day.
 
• Instructed to have glucose on hand for hypoglycemia
 
• Subjects will be instructed to consider avoiding the use of products containing acetaminophen
 
• If acetaminophen is taken, subjects will be instructed to use additional BG meter readings (they are not to calibrate with those readings) to verify their glucose levels.
 
• If acetaminophen is taken, subjects should consider exiting Auto Mode
 
• Pump has cybersecurity encryptions to prevent hacking.
 

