## Adverse Device Effect (ADE) (ISO 14155-2011)

Adverse event related to the use of an investigational medical device.

**Note 1:** This definition includes adverse events resulting from insufficient or inadequate instructions for use, deployment, implantation, installation, or operation, or any malfunction of the investigational medical device.

**Note 2:** This definition includes any event resulting from use error or from intentional misuse of the investigational medical device.

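### The severe hyperglycemia example in Protocol 11.6 judges device relatedness by the infusion set alone, and its first row conflicts with the protocol's own causality definitions and risk list

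*Protocol*

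**What the plan says.** The example in Protocol 11.6 is introduced in prescriptive terms: "A severe hyperglycemia AE with the following event description would have the following causality assessment for device relatedness". It has three rows:

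- "Improved glucose without an infusion set/site change" is *Not related*.
- "Changed infusion set with glucose improvement" is *Possible*.
- "Infusion set fell out, bent cannula, occlusion alarm" is *Causal relationship*.

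The text above the example sets out five categories and asks the site to look at everything around the event, including the device uploads. Under *Possible* it adds: "Cases where relatedness cannot be assessed should also be classified as possible".

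Protocol 11.2 applies the word device to every device used in the study. Note 2 to its ADE definition says: "This definition includes any event resulting from use error or from intentional misuse of the investigational medical device". Protocol 10.1 lists device-related routes to high glucose, among them "Sensor under-reading resulting in hyperglycemia" and "A pump error may lead to under delivery or over-delivery of insulin".

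**The concern.** The example is the only place where the protocol turns the causality categories into a concrete coding rule for severe hyperglycemia, which is a named safety item. None of its rows mentions the sensor, transmitter, pump or Auto Mode, although the pump, with its algorithm, and the sensor are the core of the system being registered. A coordinator who reads the first row as written needs only one fact, whether the set or site was changed, to reach *Not related*.

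Relatedness decides whether an event is an ADE and, if it is serious, a SADE. Under Protocol 11.7, it also decides whether the sponsor goes on to judge the event anticipated or unanticipated. If the example displaces the definitions, the device-related part of the safety results depends on a coding shortcut.

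**Working it through.** No arithmetic applies, because the plan states no figure that could be reproduced. The check sets the first row beside the passages that bear on it.

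1. **Threshold for *Not related* (11.6).** The category is for cases where a relationship can be excluded. Its criteria include that the event does not rest on a false device result and that the harm is not clearly a use error. Not all criteria need hold at once. The first row checks neither of these two; it asks only about the set or site.

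2. **Middle categories (11.6).** *Unlikely* is for cases where a device link cannot be fully ruled out, and cases that cannot be assessed go to *Possible*. The first row passes over both.

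3. ***Causal relationship* (11.6).** Its criteria include dependence on a false device result, error in use, and an effect of stopping the device. An event driven by sensor under-reading or a false calibration entry could meet one of these. The first row would place the same event at the opposite end of the scale.

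4. **Scope of device and ADE (11.2).** Sensor, transmitter and pump are all devices for this purpose, and use error counts as a device effect. The example considers only the infusion set.

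5. **Listed risks (10.1).** The closed-loop part of the table names seven routes to hyperglycemia that involve no infusion-set fault:
   - false carbohydrate entry
   - false glucose entry
   - false calibration entry
   - failure to calibrate
   - sensor under-reading
   - loss of the sensor glucose value
   - entering or leaving Auto Mode

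   The pump part adds pump error and battery failure. Section 10.1 does not say how such events resolve. That they can resolve without a set change is an inference, but a natural one, since none of them is a set fault.

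6. **How the first row could come to apply.** Table 3 in Protocol 9.2 recommends switching Auto Mode off, or changing to injections, when glucose stays above 300 mg/dL. That is also the glucose level in the 11.2 definition of severe hyperglycemia. Recovery after that step is improvement without a set change. The first row gives *Not related*, while an effect of stopping the device is one of the criteria for *Causal relationship*.

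7. **Where the coding reaches the results.** Protocol 14.7 and SAP 7.9.3 and 7.10 list the incidence of severe hyperglycemia without restriction by causality. The device-related items they name are SADE and UADE, both confined to serious events or problems. Neither document says whether the investigator's or the committee's causality is used in the tables. The two scales also differ: sites use five categories and the committee three (12.1).

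**The case against.** The strongest reply is that this is an illustration placed under general rules that point the right way. Sites must review the uploads, unassessable cases go to *Possible*, and external committee physicians can disagree with the site's classification. Malfunctions and use errors are also recorded as device deficiencies on a separate form and summarised whatever the AE causality (Protocol 13 and 14.8). These safeguards are real but partial. The committee's review *may* include severe hyperglycemia and is not stated to cover every case. On disagreement, the protocol says only that the investigator is notified. A concrete example is also likely to be followed more readily than a list of criteria that need not all be met.

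Three stronger readings are tempting, and the documents do not support them:

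- **That these events disappear from the safety results.** Protocol 11.3 requires every severe hyperglycemia to be reported as an AE, and the planned incidence is not filtered by causality. No device-related severe hyperglycemia count is named in either document.
- **That the example biases the results in one direction only.** The second row codes an event *Possible* merely because the set was changed and glucose improved, whatever the cause. That can over-count device-related events.
- **That unanticipated effects or study-level stopping would be missed.** Under 11.7 an event identified in the protocol is anticipated, and the routes above come from the protocol's own risk list. The study-level rules in 9.11.2 name UADE, device-related DKA and device-related severe hypoglycemia, not severe hyperglycemia.

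It is also fair to note that 10.1 lists hyperglycemia in general, whereas the AE requires glucose above 300 mg/dL with ketones or symptoms. Only some episodes from these routes would qualify.

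**Conclusion.** The inconsistency stands. The first row is unconditional, looks only at the infusion set, and contradicts the definitions in 11.6, the scope of device and ADE Note 2 in 11.2, and the risk list in 10.1. A site that follows it literally could code an event caused by the sensor, pump, Auto Mode or use error as *Not related*, and so leave it out of ADE classification, and out of SADE if it is serious.

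This is a risk of miscoding and not a certainty. It depends on sites applying the example ahead of the general criteria, and on the committee not reviewing or not overturning the result. The documents give neither an expected number of severe hyperglycemia events nor a share by cause, so no under-count can be calculated and none is claimed. The overall incidence of severe hyperglycemia is unaffected, as is the primary endpoint. The correction is worth making because a stated rule gives the wrong code when followed, and putting it right is cheap.

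**What to change.** Reconcile the example in Protocol 11.6 with the definitions above it:

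- Limit the first row to events that improved without a set or site change **and** where the upload review shows no pump, sensor, Auto Mode or use-error contribution, so that a relationship can be excluded.
- For all other events that improved without a set change, refer the site to the existing categories, with *Possible* where relatedness cannot be assessed.
- In the SAP (7.9.3 or 7.10), state whether investigator or committee causality defines the device-related counts.

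The cost is a short text change in the protocol, one sentence in the SAP, and a note in site training. No new data are needed, because 11.6 already requires review of the uploads. The downside is that somewhat more events may be counted as device-related.

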## 11.7. Anticipated or Unanticipated

If an AE is determined to be related to the study device the sponsor will then assess the event to determine if it is anticipated or unanticipated.

- **Anticipated:** the event is identified in the CIP; labeling; report of priors/ Investigator's Brochure (IB) or user guide.
- **Unanticipated:** the event has not been previously identified in the CIP; labeling; report of priors/IB or user guide.

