Study Stopping Rules for Entire Study	
During the study period, the following steps will be taken for:
 

• Unanticipated Adverse Device Effects (UADE)

• Device related Diabetic Ketoacidosis (DKA)

• Device related Severe hypoglycemia

 

1. Site will notify the sponsor within approximately 24 hours of receiving knowledge of the event.

2. CEC is to review and adjudicate the event.

3. CEC will provide recommendation to the sponsor on the following:

a) If enrollment and the study may continue

b) If enrollment should be stopped, while already enrolled subjects are allowed to continue in study

c) If the entire study must be stopped, including subjects who have already received study devices.

Subject Stopping Rules	Any event of DKA or severe hypoglycemia will result in withdrawal of subject from study.

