### 9.11.2. Stopping Rules for Entire Study

During the study period, the following steps will be taken for:

- Unanticipated Adverse Device Effects (UADE)
  - Device related Diabetic Ketoacidosis (DKA)
  - Device related Severe hypoglycemia
1. Site will notify the sponsor within approximately 24 hours of receiving knowledge of the event.
  2. CEC is to review and adjudicate the event.
  3. CEC will provide recommendation to the sponsor on the following:
    - a) If enrollment and the study may continue
    - b) If enrollment should be stopped, while already enrolled subjects are allowed to continue in study
    - c) If the entire study must be stopped, including subjects who have already received study devices.

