## Unanticipated Adverse Device Effect (UADE) (21 CFR 812.3(s))

Any serious adverse effect on health or safety or any life-threatening problem or death caused by, or associated with, a device, if that effect, problem, or death was not previously identified in nature, severity, or degree of incidence in the investigational plan or application (including a supplementary plan or application), or any other unanticipated serious problem associated with a device that relates to the rights, safety, or welfare of subjects.

---

*Medtronic Confidential*

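### Section 11.7 decides whether a device-related event is anticipated by name alone, while the UADE definition in Section 11.2 also tests severity and degree of incidence, and the protocol does not say which governs

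*Protocol*

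**What the plan says.** Section 11.7 sets the operating rule and names who applies it: "If an AE is determined to be related to the study device the sponsor will then assess the event". The event is anticipated if "the event is identified in the CIP; labeling; report of priors/ Investigator's Brochure (IB) or user guide", and unanticipated if "the event has not been previously identified in the CIP; labeling; report of priors/IB or user guide". Neither limb mentions how severe or how frequent the event was expected to be.

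Section 11.2 carries the UADE definition, taken from 21 CFR 812.3(s). It covers a serious device effect that "was not previously identified in nature, severity, or degree of incidence in the investigational plan or application", and adds a residual limb for "any other unanticipated serious problem associated with a device that relates to the rights, safety, or welfare of subjects".

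Section 10.1 lists the foreseen risks. None has a frequency. Some entries have severity wording, for example "Severe hypoglycemia with or without associated seizure, coma or death". Others, such as allergic reaction under the sensor and transmitter risks, have none.

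UADE is listed as a safety category in Protocol Sections 5.2.3 and 14.7 and in SAP Sections 7.9.3 and 7.10. It is also one of the triggers in Section 9.11.2 and the synopsis that lead to CEC adjudication and a recommendation on whether enrollment and the study may go on. The other triggers listed are device-related DKA and device-related severe hypoglycemia.

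**The concern.** The protocol holds two tests of what counts as foreseen, and they can give different answers for the same event. Section 11.7 is the only place that says who makes the anticipated or unanticipated call and how, so it is the text most likely to be followed in practice. A serious device effect whose name is on a list, but which turns out worse or more common than anyone described, would pass Section 11.7 as anticipated although Section 11.2 could make it a UADE.

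Two outputs depend on the answer. One is the reported UADE count, where a low figure could reflect the labelling rule rather than the absence of unforeseen serious effects. The other is the prescribed CEC sequence in Section 9.11.2. For serious device effects other than DKA and severe hypoglycemia, UADE status is the listed trigger for that sequence.

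**Working it through.** No arithmetic applies, since neither section contains a figure. The check is a comparison of the two texts, followed by a walk through the kinds of event they must sort.

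**Step 1: the two tests.**

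| | Section 11.7 | Section 11.2 (UADE) |
|---|---|---|
| Events covered | Any device-related AE, serious or not | Serious device effects and other serious problems |
| What must have been foreseen | The event, by identification only | Nature, severity and degree of incidence |
| Judged against | CIP, labeling, report of priors/IB, user guide | Investigational plan or application, with supplements |
| Decided by | The sponsor | Not stated |

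For serious events, Section 11.7 is the looser test in two respects: it drops severity and incidence, and it names a wider set of sources.

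**Step 2: does the text resolve the difference?** Section 11.7 does not mention UADE, and Section 11.2 does not refer forward to Section 11.7. No order of precedence is given. The residual limb of the UADE definition turns on the word unanticipated, and the only operating definition of that word is the one in Section 11.7.

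**Step 3: apply both tests.**

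| Device-related event | Section 11.7 | Section 11.2 |
|---|---|---|
| Serious, named in none of the sources | Unanticipated | UADE |
| Serious, named without severity, and worse than the name conveys (a systemic allergic reaction to the sensor) | Anticipated | Can be a UADE on severity |
| Serious, named with its severity, but more frequent than described | Anticipated | Can be a UADE on incidence |
| Serious, named only in the user guide | Anticipated | Depends on whether the user guide forms part of the plan or application |
| Serious, and as described in all three respects | Anticipated | Not a UADE |
| Non-serious | By name | Not a UADE |

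The tests diverge in the second and third rows and may diverge in the fourth. They agree on serious effects that nobody listed, and on serious effects that behave as described. For non-serious events the Section 11.7 label has no bearing on UADE status.

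**Step 4: trace the consequence.** An event in a divergent row that is labelled by Section 11.7 alone drops out of the UADE count. Unless it is DKA or severe hypoglycemia, it also does not set off the Section 9.11.2 sequence.

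**The case against.** The strongest reply is that Section 11.2 remains in force. It adopts the 21 CFR 812 definitions and states the UADE test in full, and Section 11.7 never claims to replace it. On that view Section 11.7 is a general sorting label, applied mostly to non-serious events. This is a fair reading, and it rules out a stronger inference that a reader might draw, namely that almost no device effect could ever count as a UADE. The documents do not support that. Serious effects named nowhere still qualify under both texts. The labeling and IFUs are supplied under separate cover (Section 18.2), and neither they nor the IB and user guide are available here, so the reach of the named list cannot be checked.

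A reader might also infer that UADE status is the only route to study-level review. It is not:

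- Section 12.1 allows the CEC to review SAEs, SADEs and severe hyperglycemia whether anticipated or not, although its wording is permissive.
- Table 4 sends SAEs to the sponsor immediately, to the authorities within 24 hours, and to the EC within 24 hours or as the EC requires.
- Table 5 has the sponsor report SAEs to the authorities within 5 working days.
- Sections 16.11 and 16.11.1 allow suspension or termination when risk is higher than first indicated, and require investigators to reassess when risks outweigh benefits.

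Nor is Section 10.1 wholly without severity. It separates hypoglycemia from severe hypoglycemia, and Section 11.3 names hospitalised cellulitis at an insertion site, so a hospitalised site infection does not illustrate the severity gap.

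What survives is narrower. The protocol gives the sponsor a working rule that omits two of the three tests in its own definition, and does not say which prevails. The other routes bring events to notice, but they neither correct the UADE count nor set off the prescribed CEC recommendation.

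**Conclusion.** The inconsistency is real and its reach is limited. A serious device effect that is named in the CIP, but is more severe or more frequent than described, could be labelled anticipated and missed as a UADE. What is affected is the UADE count and the formal CEC trigger. The primary endpoint, the sample size and SAE reporting are not.

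The number of events at risk of misclassification cannot be estimated from these documents. The 28 device-related events in 12,389 patient-days quoted in Section 4.1.2 are all device-related AEs, reported as resolved at home. They give no rate for serious device effects and should not be used to size the problem.

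The conclusion rests on two assumptions. The first is that the UADE definition lists three separate ways to be unforeseen. If an event had to be unforeseen in all three, nature alone would decide and the references to severity and incidence would do no work. The second is that the sponsor would apply Section 11.7 as written when deciding whether a serious event is a UADE, which the protocol neither says nor excludes.

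In the text available here, Section 9.11.2 indents DKA and severe hypoglycemia beneath UADE, whereas the synopsis lists all three at one level. That may be an effect of file conversion, and no weight is placed on it. If the nesting is real, UADE classification would matter more.

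**What to change.** Reconcile the two sections by adding to Section 11.7 wording of this kind:

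> For a serious device-related event, UADE status is decided by the full test in Section 11.2, that is, whether the event was unforeseen in any one of nature, severity or degree of incidence. Being named in the CIP, labeling, report of priors/IB or user guide does not by itself make such an event anticipated. For non-serious events the identified / not identified label applies as above.

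The restriction to serious events matters. If the three-part test were extended to every device-related event, ordinary skin irritation could become unanticipated simply because Section 10.1 gives no rates. The aggregate count in Section 4.1.2 cannot serve as an event-specific incidence benchmark either. Judgement on incidence will have to draw on whatever the plan or application documents provide.

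The cost is a short protocol amendment, handled under Section 16.8. No new data are collected, and the sample size and the SAP analyses do not change. The downside is that the CEC may review a few more events and the UADE count may be higher.
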